6.7.5 Management of ALT Elevations

Transient asymptomatic Grade 3 – 4 ALT elevations have been observed in approximately 1% of subjects receiving ABT-450/r-containing regimens. If a subject experiences a post-baseline increase in ALT to $> 5 \times$ ULN that is increased from a previous measurement, the subject should have a confirmatory ALT measurement performed.

If the ALT increase is confirmed to be $> 5 \times$ ULN and increased from the previous measurement, the recommendations below should be followed:

- Evaluate for alternative etiology of ALT elevation: update medical history and concomitant medications eCRF (if applicable), and obtain additional testing as appropriate.
- Manage the subject as medically appropriate.
- Repeat ALT, AST, total and fractionated bilirubin, alkaline phosphatase, and INR within 1 week. Repeat liver chemistries as indicated until resolution.
- Discontinue study drugs if any of the following is observed at any time:
 - ALT level is $\geq 20 \times$ ULN.
 - Increasing direct bilirubin, increasing INR, or onset of symptoms/signs of hepatitis.

Alternate management of ALT increases is permitted with approval of the AbbVie Study Designated Physician.

6.7.6 Creatinine Clearance

If calculated creatinine clearance (by Cockcroft-Gault formula) is confirmed to have decreased to < 50 mL/minute (in a subject with a baseline creatinine clearance of ≥ 50 mL/min), or to below 30 mL/min (in a subject with baseline creatinine clearance < 50 mL/min), medical evaluation should include a full review of current medications, including those taken on an as needed basis, those which are sold over the counter and any dietary and herbal supplements, and appropriate dose reduction or discontinuation based on impaired renal function should be done (if applicable). Ribavirin dose should be adjusted as in [Table 10](#). Alternative management of RBV dose in the setting of reduced renal function will require approval of the AbbVie Study Designated Physician.

The investigator should also consider whether drug-drug interactions with concomitant medications may have contributed to the decrease in creatinine clearance, and whether discontinuation or substitution of the possible interacting drug might be considered. For example, drug interactions between DAAs and some antihypertensive medications could potentially increase exposures of the antihypertensive, which may lead to reduction in renal function. If anti-hypertensive medications are adjusted, vital signs should be

monitored to ensure appropriate blood pressure control. Refer to Section 5.2.3 for additional information regarding drug-drug interactions.

Table 10. Dosing of RBV in Subjects with Renal Impairment

CrCl Value	RBV Dose
30 – 50 mL/min	Alternating doses, 200 mg and 400 mg every other day
< 30 mL/min	200 mg daily
Hemodialysis	200 mg daily

Note: For RBV dosing in subjects with concurrent creatinine clearance < 50 mL/min and Hb < 10 (Table 8).

If creatinine clearance improves, the site should perform all necessary readjustments of any dose modifications that have been made. If creatinine clearance improves to above the level that triggered the RBV dose reduction, the RBV dose may be increased accordingly.

The investigator should ensure that any concomitant medication changes, RBV dose reductions, and study drug discontinuations, as well as consequent related adverse events are entered into the appropriate eCRFs.

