5.5.4 Selection and Timing of Dose for Each Subject

Study drug dosing will be initiated at the Study Day 1 Visit. Ombitasvir/ABT-450/r and SOF will be dosed QD. Thus with normal dosing, 2 ombitasvir/ABT-450/r tablets and 1 SOF tablet should be taken in the morning.

RBV (if applicable) should be dosed BID, e.g., 2 or 3 tablets taken in the morning, and 3 RBV tablets should be taken in the evening. Subjects with renal impairment should receive a reduced dose of RBV, as described below ([Table 8](#)).

Table 8. Recommended Ribavirin Dosing in Chronically HCV-Infected Patients with Chronic Kidney Disease

Renal Impairment and Creatinine Clearance, mL/min	Renal Severity	RBV Dose (mg/day)
Normal (> 80 mL/min)	None	1000/1200
CKD Stage 3 (30 – 50 mL/min)	Moderate	200 alternating with 400
CKD Stage 4 (< 30 mL/min)	Severe	200

Note: Brennan et al.²⁵

All study drugs should be dosed together and administered with food.

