6.7.1 Grades 1 or 2 Laboratory Abnormalities and Mild or Moderate Adverse Events

Subjects who develop a mild or moderate adverse event or Grade 1 or 2 laboratory abnormality, other than those discussed separately in Section 6.7.4 (Management of Decreases in Hemoglobin), Section 6.7.5 (Management of ALT Elevations), and Section 6.7.6 (Management of Creatinine Clearance), may continue study drugs with follow-up per study protocol and in accordance with local standard of care.

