6.7.2 Grades 3 or 4 Laboratory Abnormalities

With the exception of Grade 3 or higher abnormalities of total bilirubin, uric acid, phosphorus, total cholesterol, triglycerides, or glucose (in subjects with a history of diabetes), if a subject experiences a Grade 3 or greater abnormal laboratory parameter during the Treatment Period, the abnormal laboratory test should be repeated. If the Grade 3 or greater abnormality is confirmed, the investigator should assess whether the abnormality can be managed medically without interruption of study drug, or whether

study drugs should be interrupted and the laboratory parameter followed until it improves. If study drugs are interrupted and restarted and the abnormality recurs, then study drugs should be permanently discontinued.

Decreases in serum hemoglobin or in calculated creatinine clearance, or elevations of serum ALT should be managed according to the guidance in Section 6.7.4, Section 6.7.5, and Section 6.7.6 below. Grade 3 or greater abnormalities of total bilirubin, uric acid, phosphorus, total cholesterol, triglycerides, or glucose (in subjects with a history of diabetes) should be managed medically as appropriate and do not require confirmation or study drug interruption unless deemed necessary by the investigator.

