6.7.4 Management of Decreases in Hemoglobin

For Subjects Not Receiving Ribavirin:

Hemoglobin decreases should be managed according to grade, based on the guidance in Section [6.7.1](#) and Section [6.7.2](#) above.

For Subjects Receiving Ribavirin:

Reductions in hemoglobin are a well characterized side effect of ribavirin exposure. If a subject receiving the standard dose of ribavirin experiences a hemoglobin decrease meeting one of the criteria outlined in [Table 9](#), a confirmatory test should be performed. If the hemoglobin decrease is confirmed, the management guidelines in [Table 9](#) should be followed. Management will be different for subjects without a history of known cardiac disease and subjects with known cardiac disease. Subjects experiencing decreases in hemoglobin that do not meet the criteria outlined in [Table 9](#) may need hemoglobin evaluations at more frequent intervals at the discretion of the investigator.

The dose of RBV should not be further modified in subjects with creatinine clearance < 50 mL/min who are receiving a reduced dose of RBV. Reductions in hemoglobin in these subjects should be managed as medically appropriate and as outlined in [Table 9](#).

Use of hematologic growth factors (such as erythropoietin or filgrastim) or blood transfusions are permitted at the discretion of the investigator. Management of hematologic growth factor therapy is the responsibility of the Investigator, and growth factors will not be provided by AbbVie.

Alternate management of hemoglobin decreases outside of these criteria is permitted with approval of the AbbVie Study Designated Physician.

Table 9.**Ribavirin Dose Modification Guidelines in Management of Hemoglobin Decreases**

Hemoglobin Value	Intervention
Subjects with Creatinine Clearance ≥ 50 mL/min	
< 10 g/L and ≥ 8.5 g/dL	Reduce RBV dose.* Study drugs may be continued. If hemoglobin increases to ≥ 10 g/dL, may increase RBV; with gradual dose increases in 200 mg increments towards original dose.
< 8.5 g/dL	Interrupt ribavirin. Manage the subject as medically appropriate. If hemoglobin increases to ≥ 8.5 g/dL, RBV may be restarted.
Additional Guidance for Subjects with History of Stable Cardiac Disease and Creatinine Clearance ≥ 50 mL/min	

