Hemoglobin decrease of ≥ 2 g/dL during any 4-week treatment period	Reduce RBV dose.* If a subsequent hemoglobin result is greater than the level that triggered the dose reduction, RBV dose may be increased; with gradual dose increases in 200 mg increments.
< 12 g/dL after a 4-week RBV dose reduction	Interrupt ribavirin. Manage the subject as medically appropriate. If subsequent hemoglobin increases to ≥ 12 g/dL, RBV may be restarted.
For Subjects with Creatinine Clearance < 50 mL/min	
< 10 g/L	Interrupt RBV. Manage the subject as medically appropriate. If hemoglobin increases ≥ 10 g/dL, RBV may be restarted. If creatinine clearance increases to ≥ 50 mL/min, refer to guidance above.

* First dose reduction of ribavirin is by 200 mg/day. If needed, second dose reduction of ribavirin is by an additional 200 mg/day. Subjects whose dose of ribavirin is reduced to 600 mg daily receive one 200 mg capsule in the morning and two 200 mg capsules in the evening.

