8.0 Patient Disposition

The number of subjects for each of the following categories will be summarized by investigator for each treatment arm and overall.

- Randomized subjects;
- Subjects who took at least one dose of study drug;
- Subjects who completed study drug;
- Subjects who discontinued from study drug;
- Subjects who completed the study;
- Subjects who discontinued from the study.

The number and percentage of subjects who discontinued study drug will be summarized by reason (all reasons) and by primary reason (per eCRF) for each treatment arm. Similar summaries will be provided for discontinuations from the study.

The number and percentage of all subjects as applicable will be summarized by treatment arm for:

- Subjects with interruptions of all study drugs for toxicity management;
- Subjects with any RBV dose modifications;
 - Subjects with RBV dose modification due to decrease in hemoglobin;

- Subjects with RBV dose modification due to decrease in creatinine clearance;
- Subjects with RBV dose modification due to other reasons;
- Subjects with any RBV dose modifications to 0 mg (i.e., RBV interruptions).

Reasons for study drug interruptions and RBV dose modifications will be presented in the CSR listings.

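### The note under Protocol Table 10 sends sites to Table 8, which has no hemoglobin rule, when the rule for low creatinine clearance with hemoglobin below 10 is in Table 9

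*Protocol*

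**What the plan says.** Three ribavirin tables in the protocol bear on this point.

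- Table 8 (Section 5.5.4) gives ribavirin dose by degree of renal impairment. At 30 to 50 mL/min the daily dose is "200 alternating with 400" mg; below 30 mL/min it is 200 mg.
- Table 9 (Section 6.7.4) covers hemoglobin decreases. It has a separate block for creatinine clearance below 50 mL/min. At hemoglobin below 10 the action is "Interrupt RBV. Manage the subject as medically appropriate", and ribavirin may be restarted once hemoglobin is back to 10 g/dL.
- Table 10 (Section 6.7.6) gives ribavirin dose in renal impairment. Its note covers the case where low clearance and low hemoglobin occur together: "For RBV dosing in subjects with concurrent creatinine clearance < 50 mL/min and Hb < 10 (Table 8".

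Section 6.7.4 deals with the same subjects in its text. It says "The dose of RBV should not be further modified in subjects with creatinine clearance < 50 mL/min who are receiving a reduced dose of RBV", and continues "Reductions in hemoglobin in these subjects should be managed as medically appropriate and as outlined in" Table 9.

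**The concern.** The note exists for one situation, a subject on ribavirin with both reduced creatinine clearance and hemoglobin below 10. Its only function is to name the table that applies, and it names one that cannot answer the question. Taken literally, it returns the site to the ordinary renal dose, while the protocol's own rule for that subject is to stop ribavirin until hemoglobin recovers.

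This is an operative dosing instruction for anemic subjects with impaired renal function, on a drug whose effect on hemoglobin the protocol treats as well known. Section 6.7.6 is a natural place for a site to start when creatinine clearance falls during treatment. That section also requires the Study Designated Physician's approval for alternative ribavirin management in reduced renal function, so a site relying on the note could think it needs permission to interrupt.

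**Working it through.** No figure in the plan has to be reproduced. The check sets the tables side by side, traces the routes a site could take, and then gives a rough size.

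**1. What each table tells a site for a subject with hemoglobin below 10 g/dL**

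| Table | Keyed on | Clearance 30 to 50 mL/min | Clearance below 30 mL/min |
|---|---|---|---|
| 8 (Section 5.5.4) | clearance only | 200 and 400 mg on alternate days | 200 mg/day |
| 10 (Section 6.7.6) | clearance or dialysis only | 200 and 400 mg on alternate days | 200 mg/day |
| 9, block for clearance below 50 (Section 6.7.4) | clearance and hemoglobin | interrupt | interrupt |

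Below 50 mL/min, Table 8 repeats the doses of Table 10, where the reader already is. A note that announces a special case for low hemoglobin and then returns the reader to the same doses makes sense only if Table 9 was meant. Section 6.7.4 confirms this by sending the same subjects to Table 9.

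**2. Difference in dose if the note is followed**

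- 30 to 50 mL/min: (200 + 400)/2 = 300 mg/day on average, against 0 mg.
- Below 30 mL/min: 200 mg/day, against 0 mg.

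**3. Routes to the rule**

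- Appendix C grades hemoglobin from below 10.0 down to 8.0 g/dL as Grade 2. Section 6.7.1 covers Grades 1 and 2 but sets aside abnormalities "other than those discussed separately in Section 6.7.4 (Management of Decreases in Hemoglobin" and the two sections after it.
- Hemoglobin below 8.0 g/dL is Grade 3 or 4. Section 6.7.2 states: "Decreases in serum hemoglobin or in calculated creatinine clearance, or elevations of serum ALT should be managed according to the guidance in Section 6.7.4" and the two sections that follow.
- Section 6.7.4 then sends subjects with clearance below 50 mL/min to Table 9.
- Only the route that starts in Section 6.7.6 and follows the note ends at Table 8.

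**4. Who could be affected**

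Exclusion criterion 16 rules out clearance below 30 mL/min, so subjects at 30 to 50 mL/min can enter, and others may fall below 50 mL/min on treatment. The same criterion rules out screening hemoglobin below the lower limit of normal, so the combination would normally arise during treatment.

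The documents do not give the share of subjects with clearance below 50 mL/min. I assume 0 to 20%. The nearest hemoglobin rates are in Table 2 of Section 3.0: 5.5% and 6.2% below 10 g/dL in subjects without cirrhosis on 12 weeks of the 3-DAA regimen with ribavirin.

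- Arm B has about 10 ribavirin subjects: 10 × 0% = 0 to 10 × 20% = 2 with low clearance.
- Expected with both conditions: 0 at the low end; 2 × 5.5% = 0.11 to 2 × 6.2% = 0.124 at the high end.

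Only cases handled from Section 6.7.6 could be misdirected, and that fraction is unknown.

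**5. The row the note should point to**

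Table 9 prints the threshold in this row, and the upper threshold in its first row, as below 10 g/L, although the restart level is in g/dL. Since 10 g/L = 1 g/dL, and Appendix C already places anything below 65 g/L (6.5 g/dL) in Grade 4, g/dL is evidently meant.

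**The case against.** The strongest reply is that the rule is not missing. It stands correctly in Table 9, Section 6.7.4 points to it, and Sections 6.7.1 and 6.7.2 lead there. To be misled, a site must bypass the hemoglobin section, follow the note, and accept a table that never mentions hemoglobin and repeats the doses just read. Investigators keep their medical judgment, and alternate hemoglobin management is allowed with the Study Designated Physician's approval. All of this stands and limits the consequence, but it does not make the note correct.

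Two stronger readings are tempting. A reader might infer that the protocol as a whole tells sites to continue ribavirin in these subjects. It does not: Section 6.7.4 and Table 9 direct interruption.

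A reader might also infer that Section 6.7.4 forbids interruption, because it says the reduced dose should not be modified further and the SAP's disposition summary (Section 8.0) lists "Subjects with any RBV dose modifications to 0 mg (i.e., RBV interruptions") among dose modifications. But the next sentence of Section 6.7.4 refers these subjects to Table 9, and the SAP category is a reporting convention that does not instruct sites. The wording could be tidier, but the documents do not support a contradiction.

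**Conclusion.** The cross-reference is wrong as written, and Table 9 is the only table that fits the note. This is a slip in a dosing instruction, not a questionable design decision. Severity is minor: the right rule is reachable by the usual hemoglobin route, and the mistaken route is narrow.

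The estimate of 0 to 0.12 cases in Arm B is illustrative and not an upper bound. It rests on the assumed 0 to 20% with low clearance, on hemoglobin rates from a different regimen at standard ribavirin dosing, and on equal anemia risk in subjects with impaired renal function. The wrong table number is certain; harm to a subject is only possible.

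Two further inferences should not be drawn. The primary analysis is not affected, because the SVR12 definition, the ITT population and the Wilson interval do not depend on the note. Nor should the estimate be extended to the larger design in SAP Section 4.2, which gives ribavirin in Arms B, C, D and E: the protocol version for that design is not among the documents, so whether it keeps the note is unknown.

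**What to change.** Once the medical lead confirms that interruption is intended:

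1. In the note under Table 10, change Table 8 to Table 9.
2. In the same clarification, correct the two Table 9 thresholds printed in g/L to g/dL, so that the corrected note leads to a usable row.
3. Optional tidy-up: Section 5.5.1 cites Table 9 for the reduced renal dose, which is in Table 10. This has little practical effect, because Section 5.5.1 states the dose and cites Section 6.7.6.

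The cost is one table number and two units, plus one more table number if the tidy-up is done. A clarification letter to sites or the next amendment would carry it. No new procedures or data are needed, and the SAP does not change.

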5.5 Treatments**5.5.1 Treatments Administered**

Each dose of DAA study drugs (ombitasvir/ABT-450/r and SOF) and RBV (if applicable) will be dispensed in the form of tablets. Study drugs will be dispensed at the visits listed in [Table 4](#).

Ombitasvir/ABT-450/r will be provided by AbbVie as 12.5 mg/75 mg/50 mg tablets. Ombitasvir/ABT-450/r will be taken orally as 2 tablets every morning which corresponds to a 25 mg ombitasvir/150 mg ABT-450/100 mg ritonavir dose QD.

SOF will be provided by AbbVie as 400 mg tablets. SOF will be taken orally as 1 tablet every morning, which corresponds to a 400 mg dose QD.

For subjects randomized to a RBV-inclusive regimen, RBV will be provided as 200 mg tablets during the Treatment Period. RBV should be dosed based on consideration of the subject's weight from Study Day 1, either 1000 mg or 1200 mg daily divided BID per local label (e.g., < 75 kg = 1000 mg daily divided BID or ≥ 75 kg = 1200 mg daily divided BID) and his/her hemoglobin test results from the Screening Visit, according to the current approved local RBV label.

For subjects with calculated creatinine clearance ≥ 30 to < 50 mL/min, RBV should be given as alternating daily doses of 200 mg and 400 mg as described in Section [6.7.6](#); [Table 9](#). Subjects will be instructed to take study medication at the same time(s) every day. All study drugs should be administered with food. Subjects will be instructed to bring in all bottles at each visit.

Following enrollment, the site will use the IRT system to obtain the study drug container numbers to dispense at the study visits specified in [Table 4](#). Study drugs must not be dispensed without contacting the IRT system, and only for subjects enrolled in the study through the IRT system. The site will also contact the IRT system to provide study drug return information for each container at the visits specified in [Table 4](#) (Section [5.5.7](#)).

At Study Day 1, subjects will be administered study drugs by the study site personnel and receive instructions for self-administration of all study drugs from Study Day 2 through the end of the Treatment Period.

All subjects who receive at least one dose of DAA who meet virologic failure criteria during treatment (Section 5.4.1.1) will be discontinued from treatment. Resistance monitoring will continue in the PT Period regardless of whether subjects opt for alternative post-study treatment.

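### The note under Protocol Table 10 sends subjects with low creatinine clearance and hemoglobin below 10 to the wrong table, away from the rule to interrupt ribavirin

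*Protocol*

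**What the plan says.** Three ribavirin tables are involved. The protocol's list of tables confirms their numbering.

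- **Table 8 (5.5.4)** gives RBV doses by renal function. The rows that matter here are "CKD Stage 3 (30 – 50 mL/min"), with 200 mg alternating with 400 mg, and "CKD Stage 4 (< 30 mL/min"), with 200 mg/day. It has no hemoglobin criterion.
- **Table 9 (6.7.4)** gives RBV changes for falling hemoglobin. Its row for clearance below 50 mL/min and hemoglobin below 10 says: "Interrupt RBV. Manage the subject as medically appropriate. If hemoglobin increases ≥ 10 g/dL, RBV may be restarted".
- **Table 10 (6.7.6)** gives RBV doses for renal impairment. Its note reads: "For RBV dosing in subjects with concurrent creatinine clearance < 50 mL/min and Hb < 10 (Table 8").

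The text of 6.7.4 covers subjects who have clearance below 50 mL/min and are already on a reduced dose. It says "Reductions in hemoglobin in these subjects should be managed as medically appropriate and as outlined in" Table 9.

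In Section 5.5.1 the renal dose switches between 200 mg one day and 400 mg the next: "For subjects with calculated creatinine clearance ≥ 30 to < 50 mL/min, RBV should be given as alternating daily doses". It refers the reader to Section 6.7.6, which is right, and to Table 9, which is not.

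**The concern.** The Table 10 note is an operative dosing instruction. It addresses the subject who has both reduced clearance and anemia, and it sits where a site adjusting RBV for renal function will be reading. It points to a table that offers a dose for that subject and away from the one that stops the drug.

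The rule it misses is a deliberate one. With clearance of 50 mL/min or more, Table 9 answers hemoglobin between 8.5 and 10 g/dL with a dose reduction and interrupts only below 8.5 g/dL. With clearance below 50 mL/min it interrupts already below 10 g/dL. The stricter threshold protects renally impaired subjects, and the misdirected note passes over it.

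**Working it through.** The protocol states no figure to reproduce. The check sets the references against the tables and compares the resulting doses.

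**1. Where each reference points**

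| Place | Subject matter | Table cited | Table that holds the rule |
|---|---|---|---|
| Note under Table 10 (6.7.6) | Clearance < 50 mL/min with Hb < 10 | 8 | 9 |
| 5.5.1 | Renal dose at clearance 30 to below 50 mL/min | 9 | 10 |
| 6.7.4 text | Hb falls at clearance < 50 mL/min | 9 | 9 |
| 6.7.6 text | Renal dose adjustment | 10 | 10 |

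Both wrong references are one number too low, which suggests numbering that was not updated. The 5.5.1 slip is harmless, because that sentence states the dose itself and names the right section.

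**2. Dose under the note as printed, against Table 9, when Hb is below 10 g/dL**

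- Clearance 30 to below 50 mL/min: Table 8 gives (200 + 400)/2 = 300 mg/day on average. Table 9 gives 0 mg/day until Hb is at least 10 g/dL.
- Clearance below 30 mL/min: Table 8 gives 200 mg/day. Table 9 gives 0 mg/day until the same restart value. Clearance below 30 mL/min is excluded at screening, so this case arises only on treatment.

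**3. Units in Table 9**

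In the text as supplied, the upper hemoglobin limit is in g/L in two rows: the first row for clearance of 50 mL/min or more, and the row for clearance below 50 mL/min. Since 10 g/L = 1 g/dL, the first row read literally asks for a value below 1 g/dL and at least 8.5 g/dL, which no result can satisfy. The second would interrupt below 1 g/dL and restart at 10 g/dL. The intended unit is plainly g/dL in both.

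**4. How many subjects**

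Entry is allowed down to a clearance of 30 mL/min. Hemoglobin below the lower limit of normal is excluded at screening, so the combination can arise only on treatment. Arm B has about 10 subjects. For scale, assume the rates of Hb < 10 g/dL in the two 12-week RBV groups of Protocol Table 2 outside the cirrhosis study (5.5% and 6.2%). Those groups were genotype 1 and took a different DAA regimen. The expected number in Arm B with Hb < 10 g/dL at any clearance is then 10 × 0.055 = 0.55 to 10 × 0.062 = 0.62. The number who also have clearance below 50 mL/min can only be smaller. The documents do not give it, and it may be zero.

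**The case against.** The best defense accepts the wrong table numbers and disputes that they matter. Sections 6.7.1 and 6.7.2 route hemoglobin decreases to 6.7.4. That section names subjects with clearance below 50 mL/min and sends them to Table 9, which has a row for exactly this group. The note states no dose itself, and a reader who turns to Table 8 for a hemoglobin rule will see that there is none. Departures from the hemoglobin guidance, and alternative RBV dosing in reduced renal function, need approval from the sponsor's study physician. All of this stands and is why the point is minor. It does not make the note right, because the table it cites does list a dose for a subject with that clearance.

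A reader might infer two stronger points that the documents do not support.

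- **That 6.7.4 contradicts itself.** It says "The dose of RBV should not be further modified in subjects with creatinine clearance < 50 mL/min" when they are already on a reduced dose, and SAP 8.0 lists "Subjects with any RBV dose modifications to 0 mg (i.e., RBV interruptions") under dose modifications, so an interruption might seem forbidden. But the SAP entry is a heading for a disposition table and defines nothing clinically. It also belongs to a SAP for about 70 subjects in Arms A to F, a wider design than the two arms of this protocol. Within 6.7.4 the very next sentence applies Table 9 to the same subjects, and Table 9 keeps reducing and interrupting apart. The natural reading is no further stepwise reduction, but interruption under Table 9.
- **That the dose is undetermined at exactly 50 mL/min.** Tables 8 and 10 label the band 30 – 50, which taken inclusively covers 50. Section 5.5.1 sets the starting rule as at least 30 and below 50, and 5.6.4 also reduces only below 50. On treatment, 6.7.6 acts for these subjects only on a confirmed fall below 50. The rule is settled, and the band label is only untidy.

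**Conclusion.** The Table 10 note is wrong as written, with minor safety relevance. For a subject with clearance below 50 mL/min and hemoglobin below 10 g/dL, the dose at stake is the one worked out above, against no RBV, for as long as hemoglobin stays under 10 g/dL. That outcome requires a site to act on the note without consulting 6.7.4. The 5.5.1 reference and the unit slips are clerical, and the context shows what is meant.

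Nothing here touches the efficacy analysis. SVR12 is a proportion per arm with a Wilson interval, and its definition does not depend on RBV dose changes. The verdict rests on reading the triggers as g/dL and on taking the Table 9 row, backed by 6.7.4, as the sponsor's intended rule.

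**What to change.** Make three wording corrections:

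1. In the note under Table 10, replace the reference to Table 8 with Table 9.
2. In 5.5.1, replace the reference to Table 9 with Table 10.
3. In Table 9, print the limit as < 10 g/dL in both rows that show < 10 g/L (clearance of 50 mL/min or more, and clearance below 50 mL/min).

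As optional tidying, write the Table 10 band as ≥ 30 to < 50 mL/min so that it matches 5.5.1.

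The cost is wording in one protocol amendment. It adds no procedures, visits or subjects, and nothing in the SAP needs to change.
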